**Table 14.1.3.2: Demographic data for ACR20 responders versus non-responders at Week 12**

Same descriptive table as above, but split up for ACR20 responders and non-responders at Week 12. See further on for the definition of ACR20.

Population: ITT.

Table to be created for the Week 12 interim analysis as well.

**Listing 16.2.4.1: Demographic data**

Listing per treatment group and per subject of all demographic parameters.

Population: safety.

**Table 14.1.3.3: Baseline laboratory data: Tabulation of abnormalities**

Frequency tabulation per lab test and per treatment group (and overall) of the baseline result, categorized as low/normal/high according to the normal ranges (see section 12.2.5). Exclude the CRP.

Population: safety.

**Table 14.1.3.4: Baseline ECG data: Tabulation of abnormalities**

Frequency tabulation per parameter (QT and QTcF) per treatment group (and overall) of the baseline result, categorized as (same as in section 12.3.5):

≤450 ms ;

]450,480] ms ;

]480,500] ms ;

>500 ms.

Population: safety.

**Table 14.1.3.5: Baseline vital signs data: Tabulation of abnormalities**

Frequency tabulation per parameter and per treatment group (and overall) of the baseline result, categorized as low/normal/high according to the normal ranges (see section 12.4.3).

Population: safety.

**Table 14.1.3.6: Baseline physical examination: Tabulation**

Frequency tabulation per CRF body system and per treatment group (and overall) of the baseline result, categorized as normal/abnormal.

Population: safety.

## 7.5. BASELINE DISEASE CHARACTERISTICS

### 7.5.1. Parameters

- Duration of RA (years) =  $\frac{(\text{date of initial diagnosis}) - (\text{screening date}) + 1}{365.25}$ , rounded to the nearest integer. If the date of initial diagnosis is incomplete, then the following rules will be applied: Missing day: use the first of the month. Missing month: use January.
- Duration of RA, categorized:
  - <0.5;
  - [0.5,2[ ;
  - [2,5[ ;
  - [5,10[ ;
  - [10,20[ ;
  - ≥20 years
- Screening and baseline CRP
- Screening and baseline CRP, categorized:
  - <0.7 x ULN;
  - [0.7,1.0] x ULN;
  - ]1.0,1.2[ x ULN;
  - ≥ 1.2 x ULN
- Change in CRP (baseline – screening)
- Screening and baseline TJC68 and SJC66
- Change in TJC68 and SJC66 = baseline – screening
- Screening and baseline DAS28(CRP) – see further sections for the definition of the DAS28(CRP)
- Change in DAS28(CRP) = baseline – screening
- Screening and baseline patient's global evaluation of disease activity (0-100 mm VAS)
- Change in patient's global evaluation of disease activity = baseline – screening
- Baseline investigator's global evaluation of disease activity (0-100 mm VAS)
- Baseline patient's pain score (0-100 mm VAS)
- Baseline HAQ-DI
- Baseline SDAI
- Baseline CDAI
- RF status, classified as positive/negative based on the upper limit of the normal range (ULN):
  - o Positive: value > ULN
  - o Negative: < value ≤ ULN
  - o Missing: value is missing for any reason.
- Anti-CCP status, classified as positive/negative based on the upper limit of the normal range (ULN):
  - o Positive: value > ULN
  - o Negative: < value ≤ ULN
  - o Missing: value is missing for any reason.
- Affected joints identification
- Prior RA medication:

- Generic names, also classified as: biological (anti-TNF or other biological DMARD), anti-TNF, other biological DMARD, conventional DMARD, NSAID, steroid, analgesic, other RA medication.
- MTX duration (study screening date – date of start of MTX + 1 day), expressed in years. If there were multiple dosing periods of MTX, then the “duration” will add up all such episodes.
- MTX duration, categorized as:
  - <0.5;
  - [0.5,2[ ;
  - [2,5[ ;
  - [5,10[ ;
  - [10,20[ ;
  - ≥20 years
- MTX dose at the start of the study, expressed in mg/week
- MTX dose at the start of the study, categorized as:
  - <10 ;
  - [10,15[ ;
  - ]15,20[ ;
  - >20 mg/week
- Steroids (as prednisolone-equivalent): total daily dose at the start of the study
- Steroids (as prednisolone-equivalent): total daily dose at the start of the study, categorized as:
  - <5 ;
  - [5,10[ ;
  - [10,15[ ;
  - [15,20[ ;
  - ≥20 mg/day.

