### 8.3.2 Inclusion Criteria

To be eligible for study entry subjects must fulfil all of the following criteria:

1. Male or female subjects who are  $\geq 18$  years of age, on the day of signing informed consent.
2. Diagnosis of RA since at least 6 months prior to Screening and meeting the 2010 ACR/EULAR criteria of RA and ACR functional class I-III.
3. Have  $\geq 6$  swollen joints (from a 66-joint count) and  $\geq 8$  tender joints (from a 68-joint count) at Screening and Baseline, and a Screening serum CRP  $\geq 0.7$  x upper limit of the normal (reference) laboratory range (ULN).
4. Have received MTX (oral or parenteral) for  $\geq 6$  months and have been on a stable dose (15 mg/week to 25 mg/week) of MTX for at least 4 weeks prior to Screening and willing to continue on this regimen for the duration of the study. Stable doses of MTX as low as 10 mg/week are allowed, when there is documented evidence of intolerance or safety issues at higher doses.
5. If taking oral steroids, these should be at a dose  $\leq 10$  mg/day of prednisone or prednisone equivalent and stable for at least 4 weeks prior to Baseline.
6. If taking non-steroidal anti-inflammatory drugs (NSAIDs), these must be at a stable dose for at least 2 weeks prior to Baseline.
7. The results of the following laboratory tests performed at the central laboratory at Screening must be within the limits specified below:

CONFIDENTIAL

- a) Hemoglobin  $\geq 10$  g/dL (International System of Units [SI]:  $\geq 100$  g/L);
  - b) WBCs  $\geq 3.0 \times 10^3$  cells/mm^3 (SI:  $\geq 3.0 \times 10^9$  cells/L);
  - c) Neutrophils  $\geq 2.0 \times 10^3$  cells/mm^3 (SI:  $\geq 2.0 \times 10^9$  cells/L);
  - d) Lymphocytes  $\geq 1.0 \times 10^3$  cells/mm^3 (SI:  $\geq 1.0 \times 10^9$  cells/L);
  - e) Platelets  $\geq 100 \times 10^3$  cells/mm^3 (SI:  $\geq 100 \times 10^9$  cells/L);
  - f) Serum ALT and aspartate aminotransferase (AST)  $\leq 1.5 \times$  ULN;
  - g) Total bilirubin level  $\leq 1.25 \times$  ULN;
  - h) Alkaline phosphatase  $\leq 1.5$ ULN;
  - i) Lipase  $\leq 1.5 \times$  ULN and amylase  $\leq 1.5$ ULN;
  - j) Creatinine clearance  $>60$  mL/min. Creatinine clearance will be calculated using the Cockcroft-Gault formula.

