**7.4. DEMOGRAPHICS AND BASELINE DISEASE CHARACTERISTICS****7.4.1. Parameters**

- sex
- age (years) as recorded in the eCRF
- age categories:
  - < 45 ;
  - [45,65[ ;
  - [65,75[ ;
  - ≥ 75 years
- year of birth: only listed
- race
- ethnicity
- height (cm)
- weight (kg)
- body mass index BMI = (weight in kg) / (height in m) (kg/m^2): the BMI will be recalculated and rounded to the nearest integer, even when already available in the database. The original BMI will not be used in that case.
- BMI categories:
  - ≤18.5;
  - ]18.5,25.0] ;
  - ]25.0,30.0[ ;
  - ≥30.0 kg/m^2

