**Table 14.2.1.1.10: ACR20 at Week 12: Tabulation versus baseline characteristics**

The table will show two methods of imputing missing values: LOCF and NRI.

Frequency tabulation of the ACR20 response rate at Week 12 per treatment group, split up according to the following baseline categories:

- Demographics:
  - Region (as used in the central randomization)
  - Country
  - Gender
  - Age categories:
    - < 45 ;
    - [45,65[ ;
    - [65,75[ ;
    - ≥ 75 years
  - BMI categories:
    - ≤ 18.5;
    - ] 18.5 , 25.0 ] ;
    - ] 25 , 30 [,
    - ≥ 30 kg/m^2
- Baseline disease characteristics:
  - Duration of RA:
    - < 1;
    - [ 1 , 2 [ ;
    - [ 2 , 5 [ ;
    - [ 5 , 10 [ ;
    - [ 10 , 20 [ ;
    - ≥ 20 years
  - Baseline CRP:
    - <0.7 x ULN;
    - [0.7,1.0] x ULN;
    - ]1.0,1.2[ x ULN;
    - ≥ 1.2 x ULN
  - Baseline TJC68: < 20, ≥ 20
  - Baseline SJC66: < 20, ≥ 20
  - Baseline DAS28(CRP): high, moderate, low, remission (see further section on DAS28 for the definition of these categories)
  - RF status
  - Anti-CCP status
  - Previous use of:
    - Biological (anti-TNF or other biological DMARD) yes/no,
    - anti-TNF yes/no,
    - other biological DMARD yes/no,
    - conventional DMARD yes/no,
    - NSAID yes/no,
    - steroid yes/no,

- analgesic yes/no,
- other RA medication yes/no.

Population: ITT.

Table to be created for the Week 12 interim analysis as well.

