#### **12.3.2. Calculated Parameters**

The QTc will always be derived during the statistical analysis, even when already available in the database. The value in the database will not be used in the analysis.

The QTc will be calculated using the following formula: Fridericia's cube-root corrected QT (Fridericia, 1920):

$$QTcF \text{ (ms)} = QT \text{ (ms)} \times \sqrt[3]{\frac{HR(bpm)}{60}}$$

The QTcF will be rounded up to the nearest integer prior to the derivation of changes and categorizations.

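### SAP 7.5.1 subtracts RA duration in the wrong order and leaves methotrexate start doses of exactly 15 and 20 mg/week without a class; classing on rounded duration or BMI would also shift subjects

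*SAP*

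**What the plan says.** **RA duration (SAP 7.5.1).** The numerator is the date of initial diagnosis minus the screening date, plus 1; the denominator is 365.25. The result is "rounded to the nearest integer. If the date of initial diagnosis is incomplete, then the following rules will be applied". Six classes follow, with cut-offs at 0.5, 2, 5, 10 and 20 years. The same list defines methotrexate duration in the opposite order: "MTX duration (study screening date – date of start of MTX + 1 day), expressed in years".

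**RA duration in the subgroup tables.** Table 14.2.1.1.10 is a "Frequency tabulation of the ACR20 response rate at Week 12 per treatment group, split up according to the following baseline categories". Its duration classes are cut at 1, 2, 5, 10 and 20 years, so its lowest class is under 1 year rather than under 0.5. Table 14.2.1.4.7 uses the same classes for the DAS28(CRP) change.

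**Eligibility (Protocol 8.3.2).** Inclusion criterion 2 requires "Diagnosis of RA since at least 6 months prior to Screening". Criterion 4 sets the standard stable methotrexate dose at 15 to 25 mg/week, with 10 mg/week allowed in documented cases.

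**Methotrexate start dose (SAP 7.5.1).** Under "MTX dose at the start of the study, categorized as" the classes are below 10; 10 up to but excluding 15; above 15 up to but excluding 20; and above 20 mg/week. Table 14.1.4.4, for the average on-study weekly dose, closes the two middle classes on the right, at 15 and at 20.

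**BMI (SAP 7.4.1).** The plan says "the BMI will be recalculated and rounded to the nearest integer, even when already available in the database", and that the original value is then not used. The cut-offs are 18.5, 25.0 and 30.0.

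**Contrast (SAP 12.3.2).** For QTcF the order of operations is stated: "The QTcF will be rounded up to the nearest integer prior to the derivation of changes and categorizations". Nothing similar is said for RA duration or BMI.

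**The concern.** A derivation rule in an SAP is an instruction to a programmer. Followed literally, the duration formula yields negative disease durations and puts the whole trial population in one class. The start-dose classes drop subjects at two doses, one of which is the lower end of the protocol's standard range.

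The rounding is a second layer. Someone who notices the negative durations and changes only the sign could still misplace subjects, because the rounded value is the only RA duration the plan defines.

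RA duration and BMI define rows in the ACR20 and DAS28(CRP) subgroup tables and are candidate covariates in the two stepwise models (Tables 14.2.1.1.11 and 14.2.1.4.8). Methotrexate start dose appears in none of these four outputs. By name it feeds Table 14.1.3.13, and probably the general baseline disease tables as well.

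**Working it through.** The plan states no figure to reproduce. The check applies its rules to test values. Let d be the number of days from diagnosis to screening. Six calendar months are 181 to 184 days, so eligible subjects have d of at least 181.

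**1. RA duration as written:** (-d + 1)/365.25, rounded.

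| d (days) | Result | Rounded |
|---|---|---|
| 181 | -180/365.25 = -0.493 | 0 |
| 184 | -183/365.25 = -0.501 | -1 |
| 1,826 | -1,825/365.25 = -4.997 | -5 |

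Every eligible d gives zero or less, so every subject falls below 0.5 (SAP 7.5.1) and below 1 (Tables 14.2.1.1.10 and 14.2.1.4.7). In the stepwise models duration is a linear term. Before rounding, the written value equals minus the correct value plus 2/365.25. Fit and p-value are therefore unchanged, but the coefficient changes sign and the odds ratio becomes its reciprocal.

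**2. Order corrected, rounding kept:** (d + 1)/365.25.

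| d (days) | Unrounded (years) | Rounded | Subgroup class, unrounded | Subgroup class, rounded |
|---|---|---|---|---|
| 181 | 182/365.25 = 0.498 | 0 | under 1 | under 1 |
| 182 | 183/365.25 = 0.501 | 1 | under 1 | 1 to <2 |
| 364 | 365/365.25 = 0.999 | 1 | under 1 | 1 to <2 |

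Of the eligible day counts below 1 year (181 to 364), only 181 stays in the lowest class. The same shift moves 1.5-2, 4.5-5, 9.5-10 and 19.5-20 years up one class, in both sets of classes.

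**3. BMI classed on the rounded value.** 25.01-25.49 rounds to 25 and drops to the class ending at 25. 29.50-29.99 rounds to 30 and rises to the class starting at 30. Exactly 18.5, rounded half up to 19, leaves the lowest class.

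**4. Methotrexate start dose.**

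| Dose (mg/week) | Class in SAP 7.5.1 | Class with Table 14.1.4.4 limits |
|---|---|---|
| 10 | 10 to <15 | 10 to 15 |
| 12.5 | 10 to <15 | 10 to 15 |
| 15 | none | 10 to 15 |
| 17.5 | >15 to <20 | >15 to 20 |
| 20 | none | >15 to 20 |
| 22.5 and 25 | >20 | >20 |

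**5. Possible size of the rounding effect.** The documents give no distributions, so these are illustrations only.
- RA duration, assumed log-normal with median 6-8 years and log-SD 0.8-1.1, truncated at 0.5 year: rounding changes the subgroup class of 10-16% of subjects. The true share under 1 year is 0.4-4%, and rounding moves essentially all of it out of that class.
- BMI, assumed normal with mean 26-28 and SD 4.5-6: 6-8% of subjects change class.

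**The case against.** The best defence has five parts.

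- **The sign slip would be noticed.** Methotrexate duration in the same list has the right order, and negative durations would stand out in any output. Table 14.1.3.7 was also due at the Week 12 interim. This makes a wrong final table unlikely, but the written rule is still wrong.
- **The SAP does not say that classes use rounded values.** Where it intends that, as for QTcF, it says so, and cut-offs of 18.5 kg/m² and 0.5 year sit oddly with integers. This stands, so the rounding point has to be conditional. The rounded reading is still the natural one: only the rounded duration is defined, and the original BMI is set aside.
- **The brackets may be an extraction error.** The text was read from PDF by a program, and Table 14.1.4.4 has no gap. They should be checked against the source. The mock tables, a separate document, may also show what was intended.
- **The models use continuous terms.** Age, BMI and RA duration enter the stepwise models unclassed, so class boundaries do not matter there. This is correct: for duration the effect is a reversed direction and some coarsening, and for BMI coarsening only.
- **The outputs are descriptive or exploratory.** This is also correct.

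A reader might infer that the under-1-year subgroup is empty under the plan as it stands. It is not: with the written sign that class holds every eligible subject, and it empties only if the sign is corrected and rounded values are used. Even then a 181-day history, or an enrolment breaching the 6-month criterion, could fall in it. A reader might also infer that the methotrexate gap distorts the efficacy subgroups or models. Start dose is not among their factors.

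**Conclusion.** Two rules in SAP 7.5.1 are wrong as written. The RA duration formula gives zero or a negative number for every eligible subject, which puts all of them in the lowest class and reverses the direction of the duration effect in the exploratory models. The start-dose classes omit exactly 15 and 20 mg/week, subject to a check of the brackets against the source PDF; this touches baseline tables only.

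The rounding problem holds if classes are assigned from rounded values, which is likely but not stated. The affected value ranges are exact. The percentages of subjects depend on the assumed distributions and should not be quoted as findings about this trial.

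The consequences are minor. The primary ACR20 model at Week 12 contains treatment, region and previous use of biologics, none of which is derived by these rules.

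**What to change.** - **RA duration:** compute (screening date - diagnosis date + 1)/365.25.
- **RA duration and BMI:** assign classes and fit models on unrounded values; round for display only.
- **Methotrexate start dose:** use the Table 14.1.4.4 limits, with the two middle classes running from 10 to 15 inclusive and from above 15 to 20 inclusive.

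The cost is a few lines of SAP wording. Demographics (Table 14.1.3.1), baseline disease characteristics (14.1.3.7 to 14.1.3.9) and both subgroup tables were also scheduled for the interim analysis, so the sponsor should confirm which rules the existing programs apply and rerun any table that followed the written ones.

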## 7.5.2. Analysis

### Table 14.1.3.7: Screening and baseline disease characteristics

Continuous parameters: descriptive statistics per treatment group (and overall). Overall p-value to compare all groups: ANOVA model with factor treatment.

Categorical parameters: frequency tabulation per treatment group (and overall). Overall p-value to compare all groups: Cochran-Mantel-Haenszel test for general association.

Population: safety, ITT, per-protocol.

Table to be created for the Week 12 interim analysis as well, but only for Safety and ITT populations.

### Table 14.1.3.8: Screening and baseline disease characteristics by region

Same descriptive table as above, but split up for the 4 geographical regions.

Population: ITT.

Table to be created for the Week 12 interim analysis as well.

**Table 14.1.3.9: Screening and baseline disease characteristics for ACR20 responders versus non-responders at Week 12**

Same descriptive table as above, but split up for ACR20 responders and non-responders at Week 12.

Population: ITT.

Table to be created for the Week 12 interim analysis as well.

**Table 14.1.3.10: Affected joints: Tabulation**

Frequency table of the detailed affected joints, separately for: tender / swollen. No formal comparisons of treatment groups.

Population: Safety.

**Table 14.1.3.11: Prior RA medication**

Tabulation of the number of prior RA medications (split up for anti-TNF biological DMARD, other biological DMARD, conventional DMARD, NSAID, steroid, analgesic, other RA medication) and the generic terms per treatment group and overall. No formal comparisons of treatment groups.

Population: safety.

**Table 14.1.3.12: Prior RA medication for ACR20 responders versus non-responders at Week 12**

Same descriptive table as above, but split up for ACR20 responders and non-responders at Week 12. No formal comparisons of treatment groups.

Population: ITT.

**Table 14.1.3.13: Prior methotrexate: Descriptive statistics**

Descriptive statistics per treatment group (and overall) of the total prior MTX duration (in years) and the MTX dose at the start of the study (mg/week).

Frequency per treatment group (and overall) of the total prior MTX duration (in years).

Frequency per treatment group (and overall) of the MTX dose at the start of the study (mg/week).

Population: Safety.

**Table 14.1.3.14: Prior steroid dose at the start of the study: Descriptive statistics**

Descriptive statistics per treatment group (and overall) of the prior steroid dose at the start of the study (mg/day prednisolone-equivalent).

Frequency per treatment group (and overall) of the prior steroid dose at the start of the study.

Population: Safety.

#### **Listing 16.2.4.2: Prior RA medication**

Listing per treatment group and per subject of the prior RA medications.

Population: safety.

## **7.6. MEDICAL HISTORY AND CONCURRENT DISEASES**

#### **Table 14.1.3.15: Medical history: Tabulation**

Frequency tabulation per treatment group (and overall) of the system organ classes and preferred terms, selecting only the medical history findings (i.e., condition no longer present at the start of the study).

Population: safety.

#### **Table 14.1.3.16: Concurrent diseases: Tabulation**

Frequency tabulation per treatment group (and overall) of the system organ classes and preferred terms.

Population: safety.

#### **Listing 16.2.4.3: Medical history**

Listing per treatment group and per subject of the medical history data findings (i.e., condition no longer present at the start of the study): original terms as well as coded terms.

Population: safety.

#### **Listing 16.2.4.4: Concomitant diseases**

Listing per treatment group and per subject of the concomitant diseases data findings (i.e., condition still present or unknown): original terms as well as coded terms.

Population: safety.

## **7.7. PRIOR AND CONCOMITANT THERAPIES**

Note that prior RA medications are presented in the section on baseline disease characteristics. They are not repeated here.

### **7.7.1. Classification of Therapies**

All prior and concomitant therapies will be allocated into exactly one of the following categories (using the analysis periods as defined in section 3.2):

- Prior only: the therapy ended before the first study treatment administration.
- Concomitant only: the therapy started on or after the first study drug administration.
- Post-treatment: the therapy started after the last study drug administration.
- Prior and concomitant: the therapy started before the first study drug administration, and ended on or after the first study drug administration.

When the start date is completely missing, the therapy is assumed to have started on the same day as the first administration of study medication.

When the end date is missing, the therapy is assumed to be still ongoing after the end of the study.

When the start date is only partially known, the missing parts will be imputed by the first day of the month/year, or the day of the first medication intake in case the nonmissing part matches.

When the end date is only partially known, the missing parts will be imputed by the last day of the month/year, or the day of the last medication intake in case the nonmissing part matches.

Imputation of start and end dates is only done for the classification into prior / concomitant / prior + concomitant. The listing will present the original start and end dates, also when incomplete. Fields like start and stop days will not be derived from imputed incomplete dates.

The relative study day of therapy start and stop will be derived as follows (only listed):

### **Start day**

= (Therapy start date) – (date of first study medication administration) + 1, when the start date of therapy is known and complete, and when the therapy start date is on or after the date of first study medication;

= (Therapy start date) – (date of first study medication administration), when the start date of therapy is known and complete, and when the therapy start date is before the date of first study medication;

= missing when the start date of therapy is unknown, missing, or incomplete.

### **Stop day**

= (Therapy stop date) – (date of first study medication administration) + 1, when the end date of therapy is known and complete, and the end date of therapy is on or after the date of first study medication;

= (Therapy stop date) – (date of first study medication administration), when the end date of therapy is known and complete, and the end date of therapy is before the date of first study medication;

= (Trial termination date) – (date of first study medication administration) + 1, when the therapy is still ongoing when the subject leaves the study; in such cases the stop day will be presented as “>XX days” in the listing;

= missing when the end date of therapy is unknown, missing or incomplete and the therapy isn't ongoing after the subject left the study.

